1.11 Will you require access to Epic to conduct this study? Yes No

The DRA's employee number must be listed on their registration form.

Please add the role of "DRA" to one study staff member on page 1 of the application.

1.12 Is the Principal Investigator a resident or trainee?

- Yes
- No

If you answer this question yes you will need to identify a Designated Records Administrator one person only.

Please check yes or no.

NOTE: Residents, Fellows, and non-MHS Personnel cannot be listed as the Principal Investigator

1.3 Study Information:

1.4 Study Information

These Questions are specifically about the adequacy of resources, are there the necessary resources to complete this study? There are two questions which focus on nursing resources. If this research will require the use of nursing resources then the Nursing Resources Form found on the IRB Home Page under forms and templates will need to be completed and attached to this research application.

1.18 Can you assure the IRB that there are adequate numbers of qualified staff to conduct this research?

Yes No

Please answer yes or no. This is an assurance to the IRB.

1.19 How will the investigator ensure that persons assisting with the research were adequately informed about the protocol and their research-related duties and functions and requirements for maintaining the confidentiality of all data?

The investigators have met and discussed the study, and plan on weekly research meetings. We discussed the project with the pulmonary rehab coordinator, who agrees to the research, but will not need to use any more time/effort towards the project. The pulmonary rehabilitation staff and coordinators are not directly involved in data collection, analysis or obtaining informed consents.

1.20 Will the PI and study staff have sufficient time to conduct and complete the research?

Yes No

Please answer yes or no. This is an assurance to the IRB.

1.21 What facilities are available to conduct the research? Are they adequate? Please describe.

Pulmonary rehabilitation cohort will be used. The rehab is located on the 3rd floor, within the pulmonary/heart and vascular clinic. Desk/offices are available with work computers in BG-3.

Please describe the facilities, i.e. lab, procedure room, chemo treatment room.

Nursing Resources:

1.22 Is this study using MetroHealth staff nurse time or labor ? (i.e. giving medications, teaching, or additional documentation)

Yes No

This is in addition to the time of the study/research nurse.

1.23 Attach Nursing Resources Form here:

Click here for [Nursing Resources form](#)

Open the form, Complete the form and save it to your files then attach it to the study by hitting the browse file and selecting the file and hitting OK.

Click here for the [MHS Policy](#)

View: 05-00 Funding Information I

5.0 Funding Information I:

All Research Projects must have an identified funding source!

5.1 Is this research externally funded? No

Check one

Research can be both externally and internally funded so you can answer yes to both 5.1 and 5.6.

5.2 Types Of External Funding:

Check all that apply.

Name _____

There are no items to display

5.3 If other, external funding please explain:

If other please describe.

5.4 Sponsor Information:

Please supply this information as your application can not be processed without it.

Name Sponsor/Agency

Address Telephone FAX Contact Person

There are no items to display

5.5 Have you received and/or submitted a Notice of Award or Contract?

Select one from drop down menu.

No

Attach notice of award.

If yes, attach your Notice of Award letter here (not your grant):

Name _____ Version _____

There are no items to display

View: 05-01 Funding Information II

5.1 Funding Information II

5.6 Is Research Internally Funded (internal funding is any MetroHealth System or MetroHealth Foundation funds):

Check one, research can be both externally and internally funded so you can answer yes to both 5.1 and 5.6.

Yes No

Copies of all RABO forms are available at:

<http://www.metrohealthresearch.org/raboforms.html>

View: 06-00 Performance Site Information

6.0 Performance Site Information:

6.1 At what sites will the study team be performing this research, (please enter information about all non-MHS sites in 5.2):

Name

[The MetroHealth System](#)

Select all that apply. If you select other please enter information about that site in question 6.2.

If this study is being done at MetroHealth where is it being done give the physical location (i.e. 8B, ED, Broadway, Old Brooklyn, PICU, Cath Lab):

Surveys will be sent electronically to patients via MyChart, or through regular US mail. The patients who may be included in the study will be the cohort of patients undergoing Pulmonary Rehab (Hamann 3rd floor).

Where is the research going to be done? What physical location on the Main campus or the community health centers?

6.2 Please provide information about other external sites here:

Name of Site Address Telephone Number

There are no items to display

Please enter contact information. Please include name of facility, address and department.

6.3 If you are doing this research at an external site does this site have an IRB?

Yes No

Select yes or no.

6.4 If the External Site has an IRB will that IRB defer review to the MHS IRB?

Yes No

This only applies if there is no IRB or if there is a legal agreement between

6.5 Attach letter from external site agreeing to permit the MHS to review this protocol:

Name	Description
------	-------------

There are no items to display

institutions permitting a reciprocal review, i.e. CASE.

Attach letter.

6.6 Has the external site granted permission for the research to be conducted?

Yes No

This applies to sites where there is no IRB and the investigator must get a letter from the site that gives permission to conduct the research at the site.

6.7 Attach letter from external site granting permission for the research to be conducted:

Name	Description
------	-------------

There are no items to display

Attach letter of support.

View: 06-01 Performance Site Information

6.1 Performance Site Information

6.8 Is MHS the lead institution of a multi-site study? Yes No

Please answer yes or no.

6.9 If yes, is there a plan to communicate information obtained through research that might be relevant to the protection of human subjects, including a plan to provide the IRB with information on unanticipated events, interim results, and protocol modifications.

Yes **No**

Please answer yes or no.

6.10 Please give a detailed explanation of the above plan:

This plan must give the IRB enough information to decide if

6.11 Will the Principal Investigator conduct this study at any location outside the United States of America?

Yes No

the plan is appropriate and adequate.

Answer these questions only if there are research sites outside the USA.

6.12 Country, City, and address:

Country Address of Research Facility

There are no items to display

Give country and location.

View: 07-00 Research Objectives and Background

7.0 Research Objectives and Background:

7.1 * ABSTRACT: Please give the IRB a 500 word Abstract that contains the specific objectives of the study.

Background:

Sleep disorders including poor quality of sleep are common in patients with heart disease, chronic obstructive pulmonary disease (COPD) and, possibly, other chronic lung disorders. These patients complain of difficulty sleeping; sleep fragmentation, often related to symptoms such as cough, sputum production or shortness of breath. Patients with COPD and heart failure commonly have other abnormalities such as nocturnal oxygen desaturation that may further worsen sleep disturbances.

Moreover, sleep disordered breathing (SDB), like obstructive sleep apnea syndrome (OSA), has been linked to higher morbidity and mortality if COPD is present (Overlap syndrome). In patients with COPD and heart failure, cardiac-pulmonary rehabilitation (CP-R) has important health benefits such as improvement in symptoms, exercise tolerance, and quality of life. However, the effect of CP-R on sleep quality is controversial. Disturbed sleep is associated with frequent exacerbations, increase in the severity of disease and increased mortality in COPD and heart failure patients. Sleep quality is a good predictor of quality of life in patients with stable COPD.

We hypothesize that CP-R results in improved sleep quality in patients with chronic lung and heart disease which may be an important contributor to improved health outcomes after CP-R

This is your abstract also known as a synopsis from an industry sponsored study. Please limit to 500 words.

Goals and objectives:

The purposes of this study are to:

- 1) Evaluate the effect of CP-R on sleep quality in patients with chronic lung and heart diseases.
- 2) Determine the longevity of sleep quality improvement by conducting a follow-up survey
- 3) Determine if sleep quality impairment correlates with positive screen for sleep apnea.

7.2 * What are the specific aims of this study i.e. what are the question(s) this research intends to answer? Provide at a maximum 3 primary and 3 secondary aims.

Primary aims:

1. Does cardiac-pulmonary rehabilitation (CP-R) lead to improved sleep quality?
2. Does the improvement in sleep quality persist after 3 months?
3. Is sleep impairment associated with positive screen for sleep apnea?

Secondary aims:

1. Does the improvement in sleep quality correlates with improvement in excessive daytime sleepiness, health related quality of life as determined by COPD assessment test score for COPD patients, and short form health survey-36 for cardiac patients
2. Does the improvement in health related quality of life persist after 3 month post pulmonary rehabilitation.

7.3 Please provide a summary of the present knowledge relevant to the research and make citation to any applicable scientific literature:

In patients with chronic lung and heart diseases, CP-R has important health benefits such as improvement in symptoms, exercise tolerance, and quality of life.(1) However, the effect of CP-R on sleep quality is controversial. Disturbed sleep is associated with, frequent exacerbations, increase in the severity of disease and increased mortality in COPD.(2) Sleep quality is a good predictor of quality of life in patients with stable COPD.(3) Increase in physical activity improves sleep in healthy individuals.(4) However, there has been little investigation into non-pharmacological methods to improve sleep quality in patients with COPD. It is also uncertain, how long the beneficial effects of pulmonary rehabilitation on sleep quality, if any, usually last. In an observational study, CP-R was associated with a statistically significant improvement in sleep quality.(1) Other researchers did not find any significant benefit of CP-R on quality of sleep.(5, 6) Due to lack of robust data, we sought to find the effect of CP-R on sleep quality.

8.4 * Please specify in detail the methods and procedures that are involved in this research:

Methodology:

Study Population:

This study will collect prospective data from patients being referred to Metrohealth's Pulmonary rehabilitation center.

If this field is not completed your protocol will not be reviewed. Do not enter N/A. Please describe what methods and procedures will be involved in this research.

Data collection plan:

The study will use data from questionnaires filled by patients before and after completion of pulmonary rehabilitation. A 3-month follow up survey using the same questionnaires will be conducted. The questionnaires that will be used include Pittsburgh sleep quality index (PSQI), Epworth sleepiness scale (ESS), Berlin questionnaire, COPD assessment test, Short form health survey-36 (SF-36), hospital induced anxiety and depression scale (HADS) and insomnia severity index (ISI). The questionnaires will be sent to the patients either through MyChart messaging or direct mail with a memo cover-sheet explaining the research study and voluntary participation. The surveys will be available to the participants through MyChart for four weeks after being sent out to give them ample opportunity to participate. The survey will not pop up each time with MyChart login but patients who have not filled the questionnaires will get a weekly reminder to complete the questionnaires when they login to MyChart. However, if the patient declines to participate in the study, the survey will not pop up again and no reminder will be sent. Since the questionnaires are being used to track changes before and after pulmonary rehabilitation, the participants will not be able to take the survey more than once at each point (beginning, end and 3-months post completion of pulmonary rehabilitation). All patients regardless of contact method (via mail or MyChart) will be able to bring printed and filled questionnaires on Day 1 of pulmonary rehabilitation. However, if a MyChart user prefers to fill the questionnaires online through MyChart, s/he will be able to do so. Follow up surveys at the end of pulmonary rehabilitation and 3-months post-completion will be returned via mail or MyChart depending on whether patients have signed up for MyChart or not. For MyChart users, the questionnaires will remain

available for four weeks at each point, as stated earlier. A copy of all the questionnaires being used in the study and the memo cover-sheet will be uploaded with IRB application. We will collect existing data for patients who consent to participate in the study including type and severity of disease. If the patient does not consent to the study, no data will be collected.

The de-identified data will be stored in a secure Health Insurance Portability and Accountability Act (HIPAA) compliant database.

8.5 Does this study only involve the use of existing/retrospective data/specimens?

No

Check yes or no.

8.6 Describe in detail the study design also known as the experimental flow.

Include all study procedures a subject will go through, in order of sequence and timing, including frequency of visits, duration of visits, length of subject participation etc. Please Note this needs to be written for an educated person who is not an expert in the field, do not exceed 300 words:

For the patient who have signed up for MyChart and are scheduled to start pulmonary rehabilitation, questionnaires including Pittsburgh sleep quality Index (PSQI), Epworth sleepiness scale (ESS), COPD assessment test (CAT), Short form health survey-36 (SF-36), Hospital anxiety and depression scale (HADS), insomnia severity index (ISI) and Berlin Questionnaire will be sent using MyChart. A recruitment letter will also accompany the questionnaires. For the rest of the patients, the questionnaires will be mailed. Questionnaires will be accompanied by a non-return cover memo. The packet will have the subject's unique patient identifier code on it only (no PHI).

Patient will then return the filled questionnaires on Day 1 of cardiac and pulmonary rehabilitation. However, MyChart users will have the option to return the surveys online through MyChart prior to starting pulmonary rehabilitation if they wish to do so. The rest of the patients will need to print out the questionnaires. Another patient packet including the same unfilled questionnaires with a stamped return envelope will be sent to MyChart non-users at the end of pulmonary rehabilitation and then after 3 months.

For MyChart users, MyChart will be used to send the unfilled surveys at the end of pulmonary rehab and after 3 months of completion.

It will take 40-45 minutes to complete all the questionnaires each time. The completed questionnaires will be stored in the PI's office (lock protected). Questionnaire results will be used in research database. Initial consent to participate is for the entire study. We will collect existing data for patients who consent to participate in the study including type and severity of disease as stated in non-return cover memo. For non-consenting patients, no data will be collected.

This is also known as NIH Experimental Procedure section or Clinical Trial Procedure/Experimental Flow section. Do not just attach documents in response to this question you must do a study design summary for IRB Review.

8.7 Please attach study design/subject visit schedule here:

Name	Description
Study Design History	

If you have an electronic schedule of study visits and/or procedures please attach here.

View: 09-00 Inclusion/Exclusion Criteria

9.0 Inclusion/Exclusion Criteria:

9.1 What are the inclusion criteria? Put this information in bullet form:

Inclusion criteria:

- Age > 18 years
- Patient who are willing to participate in follow-up survey 3 months after completion of PR.
- Patients who complete rehabilitation for at least 8 weeks.

Please list inclusion criteria.

9.2 What are exclusion criteria? Put this information in bullet form:

Exclusion criteria:

- Not meeting inclusion criteria

Please list exclusion criteria.

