9.4 Will you exclude women and minorities, or persons under 21 from enrollment?

No

Check yes or no.

9.5 If yes, which groups are you excluding? Provide justification for your decision.

List groups to be excluded then provide justification.

9.6 Attach Documents:

Name Description
There are no items to display

If you are unable to fit your answers in the text boxes provided please attach as a word document.

View: 10-00 Risk/Benefits

10.0 Assessment of Risk I:

10.1 Identify and distinguish between those procedures that are standard versus those that are experimental. Include the frequency and duration of each activity and the total length of subject participation:

The questionnaires including Pittsburgh sleep quality index, Epworth sleepiness scale, Berlin questionnaire, Health related quality of life questionnaires (Short form health survey-36 (SF-36) for cardiac patients and COPD assessment test for COPD patients), and hospital anxiety and depression scale and insomnia severity index (ISI) will be used for research purpose.

Patient will be asked to fill the questionnaires at baseline (start of pulmonary rehab), at completion of pulmonary rehabilitation and 3 months after completion of pulmonary rehabilitation. It will take 40-45 minutes to complete the questionnaires/ surveys each time.

All the patients will complete standard pulmonary rehabilitation as prescribed by the physician.

10.2 Describe any therapeutic alternatives to the research that may exist. How are they different from those procedures that subjects would normally undergo? Patients may elect not to participate in the survey study.

10.3 What are the outcome variables and how will they be analyzed? What are the statistical and analytical methods that will be used? *Note this section can be copied from the NIH Grant Application or from the Statistical and Analytical Methods section of the industry trial protocol.*

We will analyze the data using SPSS and STATA. The primary outcome measure will be the change in individual Pittsburgh sleep quality index scores at the beginning, end and after 3-months of cardiac and pulmonary rehabilitation. We will also screen patients for sleep apnea prior to starting rehabilitation using Berlin questionnaire.

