
Subject Age Range

18 - 64

65 - 89

90+

Check all that apply.

12.2 * Will the study enroll vulnerable subject groups? Check yes or no.

Yes

* Will you be enrolling Children?

Yes No

* Will you be enrolling Pregnant Women and/or Fetuses?

Yes No

* Will you be enrolling decisionally impaired subjects?

Yes No

* Will you be enrolling Prisoners? Yes No

12.3 Please identify any vulnerable populations participating in the study: Check all that apply.

Vulnerable Populations

Poor / Uninsured

Elderly

Employees

Students

Minorities

12.4 If you selected "other" above please describe: Please describe other.

If you are going to enroll any vulnerable populations please describe the safeguards you will put in place to protect these vulnerable Populations.

Please enter a detailed plan.

12.5 All subjects will be treated equally. The participants will consent to study by bringing questionnaire forms on the first day of their cardiac-pulmonary rehabilitation visit. All subjects will be aware that participation is completely voluntary.

View: 13-00 Recruitment I

13.0 Recruitment I:

All external advertisements (for radio, print media or TV) must be approved by MHS Communications Department prior to submission to the IRB so the IRB can see the final advertisement or script. All Advertisements on the MIV or On Hold messaging must be approved by the IRB before they are placed. You may not advertise a study which is not approved by the IRB. Please note that all studies which have a contract which an external sponsor must have that contract signed before any advertising can be done.

13.1 Recruitment Methods/Sources:

Name
Research Match
Other

Check all that apply.

13.2 If "Other" checked in 13.1 please explain:

Patients who are anticipated to begin pulmonary rehabilitation will be approached via MyChart or regular mail to voluntarily participate in the study.

Please explain what other means.

13.3 Describe in detail all recruitment strategies for each subject group (as listed in Section 11.0) selected for this research:

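### Section 9.1 makes completing at least 8 weeks of rehabilitation an entry criterion, which cannot be judged when patients enter and, applied literally, would remove about half of the baseline records for primary aim 3

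*Protocol*

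**What the plan says.** **Entry rule.** Protocol section 9.1 has three inclusion criteria, the third being "Patients who complete rehabilitation for at least 8 weeks". Section 9.2 has one exclusion criterion: "Not meeting inclusion criteria". Section 9.3 has the investigators judge eligibility against these criteria and gives no time point for doing so.

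**Timing of consent and baseline data.** Section 12.5: "The participants will consent to study by bringing questionnaire forms on the first day of their cardiac-pulmonary rehabilitation visit". Section 8.6: "Patient will then return the filled questionnaires on Day 1 of cardiac and pulmonary rehabilitation", with MyChart users free to respond online beforehand. Section 8.4 keeps each MyChart survey open for four weeks. On the sleep apnea screen, section 10.3 says: "We will also screen patients for sleep apnea prior to starting rehabilitation using Berlin questionnaire".

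**Who counts as a participant.** Section 8.6 says "Initial consent to participate is for the entire study" and "For non-consenting patients, no data will be collected". Sections 11.1 and 13.3 put programme completion at about 50%. Section 13.3 gives that rate, together with non-return of follow-up forms, as the reason for approaching 80 patients to obtain 27. Section 11.2 enters 80 both as the number to be approached and as the anticipated enrolment at the site.

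**Aims.** Section 7.2 lists three primary aims: whether rehabilitation improves sleep quality (aim 1), whether the improvement lasts 3 months (aim 2), and whether impaired sleep goes with a positive sleep apnea screen (aim 3). The SAP gives a paired t-test and a sample size for the before/after change. It mentions neither aim 3 nor the Berlin questionnaire. Neither document defines an analysis set.

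**The concern.** An entry criterion has to be decidable at entry. Completing 8 weeks is decided about two months after the patient has consented and, for most patients, after the baseline forms are in. The condition therefore works as a filter applied afterwards, and the filter falls on every aim.

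For aim 1 this matters little, because a before/after pair needs an end-of-programme form in any case. Aim 3 is different. If it relates baseline PSQI to the baseline Berlin result, a patient who later leaves the programme has already supplied everything the analysis needs. Excluding that patient costs precision. It also selects the sample on a later event that may itself be related to sleep or to apnea risk, and the documents give no basis for judging the direction of any resulting bias.

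There is also a problem of reproducibility. One analyst following sections 9.1 and 9.2 would drop non-completers from aim 3, and another following sections 8.6 and 13.3 would keep them. Both could claim to have followed the protocol, and they would report a primary aim on different samples.

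**Working it through.** **1. The plan's own figure.** Inputs from section 10.3 and the SAP: mean paired difference 3, SD of differences 4.6, type I error 0.05 (sidedness not stated; two-sided assumed), power 0.90. For a paired t-test the noncentrality is (3/4.6) × √n. At n = 27 it is 0.652 × 5.196 = 3.39 on 26 degrees of freedom, and the power is 0.903. At n = 26 the power is 0.892. So 27 pairs reproduces. The entry rule does not alter it, because patients who leave early would not be expected to supply the second member of the pair.

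**2. How section 13.3 treats non-completers.** 80 approached × 0.50 = 40 completers. Reaching 27 pairs then needs 27/40 = 67.5% of completers to return the follow-up forms. This count starts from people who have not yet completed and subtracts those who do not, so non-completion is attrition. Sections 9.1 and 9.2 make the same people ineligible. The two treatments differ.

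**3. Loss for aim 3 under the literal rule.** Let p be the completion rate among patients who return baseline forms. The share of records lost is 1 − p. With a similar SD and a similar Berlin split in completers and non-completers, the standard error is proportional to 1/√n, so it grows by the factor 1/√p.

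| p | Source | Records lost | SE ratio 1/√p |
|---|---|---|---|
| 0.40 | assumed | 60% | 1.58 |
| 0.50 | sections 11.1, 13.3 (programme-wide) | 50% | 1.41 |
| 0.60 | assumed | 40% | 1.29 |
| 0.70 | assumed | 30% | 1.20 |

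These ratios do not depend on how many baseline forms come back.

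**4. Illustration in absolute terms.** The documents name no test for aim 3. Assume a comparison of mean PSQI between Berlin-positive and Berlin-negative patients. The 95% confidence interval half-width in SD units is t(0.975, N−2) × √(1/n₁ + 1/n₂). At 50% completion:

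| Baseline forms returned (assumed) | Berlin split (assumed) | All records | Completers only |
|---|---|---|---|
| 80 of 80 | 50:50 | N = 80: 0.45 SD | N = 40: 0.64 SD |
| 80 of 80 | 30:70 | N = 80: 0.49 SD | N = 40: 0.70 SD |
| 56 of 80 (70%) | 50:50 | N = 56: 0.54 SD | N = 28: 0.78 SD |

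For the first row: 1.991 × √(1/40 + 1/40) = 0.445, and 2.024 × √(1/20 + 1/20) = 0.640.

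**The case against.** The strongest reply is that the third bullet was only ever meant to define who enters the before/after comparison and sits under the wrong heading. Much of the text supports this. Consent covers the whole study, only non-consenting patients are barred from data collection, section 13.3 builds non-completion into the 80, and the benefits text in section 10 speaks of screening the rehabilitation cohort. This reply stands as an account of likely intent. It does not remove the problem, because sections 9.1 and 9.2 are the operative eligibility rule and say otherwise.

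Four stronger readings are tempting, and the documents do not support them.

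- *That half of the aim 3 data will be lost.* No passage says non-completers' forms are discarded. The loss follows only if the rule is applied as written. The 50% is a programme-wide rate, and patients who agree to a 3-month survey may complete more often.
- *That aim 3 is expressly a baseline analysis whose data are all in by Day 1.* Section 7.2 does not restrict it to baseline, and the same questionnaires go out at all three time points. The baseline reading is an inference, a natural one, from the Berlin screen preceding rehabilitation. The four-week MyChart window also lets some baseline forms arrive after Day 1, though still before week 8.
- *That section 10.1 contradicts the 50% rate.* Its sentence "All the patients will complete standard pulmonary rehabilitation as prescribed by the physician" answers an item asking which procedures are standard and which are experimental. It is best read as saying that rehabilitation is usual care, and it makes no forecast of completion.
- *That the aim 1 test or its sample size is wrong.* Both stand, and section 8.4 already frames the data as collected before and after completion.

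A study-design attachment is listed at section 8.7 but is not in the text available. The statement that no analysis set is defined applies to the text that is.

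**Conclusion.** The point holds and should be fixed. A condition that can only be judged at least 8 weeks later is listed as an entry criterion, and it conflicts with sections 8.6 and 13.3 on who is in the study. If it is followed as written, a primary aim loses usable records to a later event: about half of them, with a standard error about 1.41 times larger, at 50% completion. Over assumed completion of 70% to 40% the loss is 30% to 60% and the ratio 1.20 to 1.58.

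The size rests on three assumptions: that the rule is applied literally, that aim 3 uses baseline PSQI and Berlin, and that completers and non-completers have similar variability and a similar Berlin split. Confidence is high on the timing mismatch and lower on the size of the loss, since the completion rate among respondents is not given. For aim 1 only the scope of the conclusion is affected: the paired test describes patients who finish and return both forms, which is narrower than the question in section 7.2.

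**What to change.** 1. Move the 8-week bullet out of section 9.1 and label it as the definition of the before/after (aim 1) analysis set. Reconcile sections 9.1 and 9.2 with 8.6, 11.2 and 13.3.
2. Add to section 10.3 and the SAP: *Aim 3 uses all consented patients with baseline PSQI and Berlin, whether or not they complete rehabilitation.*
3. State in the same places that the aim 1 paired t-test describes patients who complete at least 8 weeks and return both forms, and limit the aim 1 conclusion to them. Report the number of non-completers and their baseline PSQI.

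The cost is wording in these sections and the SAP and a short addition to the report. Section 16.16 already provides for tracking completion by chart review, and baseline PSQI is already collected, so no new data, contacts or visits are needed. Rehabilitation itself is untouched, and the 27 pairs and power of 0.903 stay as they are. The one downside is a narrower aim 1 conclusion.
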